### **1.3 Benefit/risk and ethical assessment**

End stage renal disease (ESRD) patients have significantly higher mortality rates compared to non-dialysis populations. Recent data from the USRDS database finds that the annualized death rates for all ESRD patients is approximately 23.7% with cardiac disease accounting for 40% of that number. Further analysis demonstrates that while the majority of ESRD patients have well defined risk factors for coronary disease, the cause of death is not due to atherosclerotic disease or myocardial infarction, but rather due to cardiac arrhythmias and sudden death. Current estimates indicate that up to 35% of deaths among chronic ESRD patients are due to sudden cardiac death (SCD). Any maneuvers to reduce dialysis-related arrhythmias has the potential to significantly reduce the cardiovascular mortality among ESRD patients.

Potential benefits of study participation include:

- 1) Reduction in overall SCD rates
- 2) Potential for reduction in atrial fibrillation sequelae, including but not limited to embolic stroke, myocardial infarction, ischemic bowel disease, and acute critical limb ischemia

Potential risks associated with study participation include:

- 1) Excessive study treatment-associated hypokalemia, with potential exacerbation of arrhythmia
- 2) Risk for hypokalemia-associated muscle weakness, with risk for fall, etc.
- 3) Risk for local chest wall infection from insertion of the cardiac loop recorder device.

The discussion of risks and benefits to participating in the ADAPT trial and its goal of fine-tuning dialysate electrolyte composition highlights both the pressing need and difficulty of electrolyte management among ESRD populations. Based on available data (as presented in

[Section 1.1](#)) and the risk mitigation strategies incorporated in the study design, the benefit-risk assessment favours the initiation of the ADAPT trial.

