**Table 1 Study Plan and Schedule of Assessments**

Study Period / Visit	Screening	ILR Insertion by EP cardiologist	Baseline/ Randomization	New Dialysate Accommodation Period 1	Treatment Phase 1	Cross-over	New Dialysate Accommodation Period 2	Treatment Phase 2	ILR Removal by EP cardiologist	End of Study	Reference to Protocol Section
Study Week (Wk) [* , ** or ***]	-4 to -3**	-2*	1**	1 & 2**	3 to 10**	11**	11 & 12**	13 to 20**	21-22*	22-23***	
Study Day (D)	-28 to -15	-14	1	1 to 14	15 to 70	71	71 to 84	85 to 140	Between D141 and D155	Within 1 to 14 days after ILR Removal	
Blood samples for PBUTs [3]					X						4.2.1
Day of the Week			M/T	M/T	M/T	M/T	M/T	M/T			
Local laboratory Mg ++ promptly before dialysis end) [4]				X	X		X	X			4.2.1
Adverse event recording & review [8]				X	X	X	X	X	X	X	6.4
Serious Adverse event recording & review [9]	X	X	X	X	X	X	X	X	X	X	6.4
Concomitant medication	X	X	X	X	X	X	X	X	X	X	5.2.5, 7.7
Local laboratory Mg ++ promptly before dialysis end) for muscle cramping [5]				X	X		X	X			4.2.1

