**Table 1 Study Plan and Schedule of Assessments**

Study Period / Visit	Screening	ILR Insertion by EP cardiologist	Baseline/ Randomization	New Dialysate Accommodation Period 1	Treatment Phase 1	Cross-over	New Dialysate Accommodation Period 2	Treatment Phase 2	ILR Removal by EP cardiologist	End of Study	Reference to Protocol Section
Study Week (Wk) [* , ** or ***]	-4 to -3**	-2*	1**	1 & 2**	3 to 10**	11**	11 & 12**	13 to 20**	21-22*	22-23***	
Study Day (D)	-28 to -15	-14	1	1 to 14	15 to 70	71	71 to 84	85 to 140	Between D141 and D155	Within 1 to 14 days after ILR Removal	
Pregnancy Test for Females of Childbearing Potential	X										

Abbreviations: AE=adverse event; Ca=calcium; ECG=electrocardiogram; EP=electrophysiologist; ILR=insertable loop recorder; K=potassium; Mg++=magnesium; PBUTs=protein-bound uremic toxins [including p-Cresol sulfate [PCS], indoxyl sulfate, and asymmetric dimethylarginine [ADMA)]; SAE=serious adverse event

\*Performed on any day. (Note: ILR placement needs to be one week prior to baseline, which starts on Mondays or Tuesdays after each long dialysis weekend.)

\*\*Performed weekly, on Mondays or Tuesdays after each long dialysis weekend. (Note: Screening ICF can be obtained on any dialysis day, but all other procedures need to be performed on Monday or Tuesdays after the long dialysis weekend. Additionally, consenting may be conducted several weeks prior to other study procedures depending on the need for a prohibited medication washout or whether the consenting process occurred on a day other than the Monday or Tuesday after the long dialysis weekend.)

\*\*\*Performed on any dialysis day

[1] K+ Piccolo POCT (utilizing full renal panel) are performed pre-dialysis, on a Monday or Tuesday after the long dialysis weekend, twice during the Screening period, and weekly during the treatment period (both 2-week accommodation periods and 8-week Treatment phases). Note: K+ Piccolo POCT may be performed several weeks after consenting depending on the need for a prohibited medication washout or whether the consenting process occurred on a day other than the Monday or Tuesday after the long dialysis weekend.

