#### **4.1.9 Insertion of the Cardiac Loop Recorder (Week -2)**

Patients who have completed the screening assessments and are willing to proceed with study participation will be referred to a cardiac electrophysiologist (EP) or qualified implanter who is

trained and experienced in the placement of the LINQ device. It is anticipated that arranging for placement of the device (including scheduling and actual implantation) will take approximately 1-2 weeks, but may take up to 30 days. Please contact the sponsor if ILR placement will take longer than 30 days after the last qualifying Piccolo POCT K+ System Measurements. The sponsor will determine on a case-by-case basis if an additional Piccolo POCT K+ System Measurement is required prior to Baseline.

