### **Post-LINQ Device Insertion**

For 2 weeks after LINQ device insertion, patients will be given time to heal and adapt to the device. During this 2-week blanking period, the device will measure continuous cardiac data, but it will not be interrogated and will not be used for analysis. During this blanking period, Medtronic will train study staff on how to interrogate and transmit LINQ device data, which will be sent to the Medtronic Monitoring Service; refer to the data flow shown in Figure 9.

After the 2-week ILR post-insertion recovery period, patients will be randomized to one of two treatment sequences, as described in [Section 3.5](#). The day of randomization will be denoted as Study Day 1 and will also mark the start of Treatment Phase 1.

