## **6.1 Definition of Adverse Events**

An adverse event is the development of an undesirable medical condition or the deterioration of a pre-existing medical condition following or during exposure to a pharmaceutical product, whether or not considered causally related to the product. An undesirable medical condition can be symptoms (e.g., nausea, chest pain), signs (e.g., tachycardia, enlarged liver) or the abnormal results of an investigation (e.g., laboratory findings, electrocardiogram). In clinical studies, an AE can include an undesirable medical condition occurring at any time, including run-in or washout periods, even if no study treatment has been administered.

The term AE is used to include both serious and non-serious AEs.

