#### **6.4.3 Variables**

The following variables will be collected for each AE:

- AE (verbatim)
- The date when the AE started and stopped
- Intensity

Adverse Event intensity will be assessed according to the following categories:

- mild (awareness of sign or symptom, but easily tolerated)
- moderate (discomfort sufficient to cause interference with normal activities)
- severe (incapacitating, with inability to perform normal activities)
- Whether the AE is serious or not
- Investigator causality assessment /relationship to the study drug (yes or no)
- Action(s) taken with regard to the study drug
- AE caused the patient's withdrawal from study (yes or no)
- Outcome.

In addition, the following variables will be collected for SAEs:

- Date AE met criteria for serious AE
- Date Investigator became aware of SAE

- Reason for assessing the AE as serious
- For hospitalizations:
  - Date of hospitalization
  - Date of discharge
- For AEs with a fatal outcome:
  - Date of death
  - Probable cause of death
  - Autopsy performed and finding(s)
- Causality assessment in relation to study procedure(s)
- Causality assessment in relation to other medication
- Description of SAE.

Note: It is important to distinguish between serious and severe AEs. Severity is a measure of intensity whereas seriousness is defined by the criteria outlined in [Section 6.2](#). An AE of severe intensity would not necessarily qualify as serious. For example, nausea that persists for several hours may be considered severe, but not a SAE unless it meets the criteria provided in [Section 6.2](#). On the other hand, a stroke that results in only a limited degree of disability may be considered a mild stroke but would be a SAE if it satisfies the criteria provided in [Section 6.2](#).

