#### **8.5.6 Safety Analyses**

Lokelma-induced hypokalemia will be evaluated based on the total number of hypokalemic events defined as PiccoloPOCT or laboratory-measured K+ of < 3.5 mEq/L.

The incidence of dialysis-related hypokalemia, hypomagnesemia, hypophosphatemia, and low calcium will be evaluated based on the number of events promptly prior to the termination of dialysis where a PiccoloPOCT measurement of K+ is < 2.0 mEq/L OR Ca++ is < 7.0 mEq/L, OR Mg++ is < 2.0 mg/dl, OR a PO4 level is < 3.0 mEq/L. All episodes where a specific electrolyte falls below the above listed threshold will be considered an “event” for that electrolyte. The total number of “events” will be recorded during the 8-week Treatment Phase-1 and the 8-week Treatment Phase-2 cross-over periods and compared between the treatments.

Safety will also be assessed in terms of the frequency of AEs, SAEs, and withdrawals due to AEs, with focus on treatment-related events. Appropriate summaries of these data will be presented by treatment group and/or study period.

Adverse events will be coded using the Medical Dictionary for Regulatory Activities (MedDRA) system organ class (SOC) and preferred term (PT). A treatment-emergent AE

(TEAE) is defined as an AE with the start date on or after the first dose date and up to (and including) 14 days after the last dose date in each of study periods when patients received 3K Bath with Lokelma. However, when patients received 2K Bath without Lokelma, A treatment-emergent AE (TEAE) is defined as an AE with the start date on or after the first visit date and up to (and including) 14 days after the last visit date in each of study periods. Only TEAEs will be included in table summaries.

The number and percentage of participants experiencing AEs, SAEs, AEs that led to withdrawal, AEs that led to death, and the number of such events, will be summarised by SOC, PT, and treatment group and study period. The number and percentage of participants experiencing AEs will further be summarised by intensity and will be presented with the number of events at each level of intensity.

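### Non-serious harms of loop-recorder implantation that start before Day 1 are never recorded, and serious ones reach listings but no adverse event table

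*Protocol*

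**What the plan says.** - **Named risk.** Protocol 1.3 gives three risks of participation. The third is "Risk for local chest wall infection from insertion of the cardiac loop recorder device". Removal is not named.
- **Timing of implantation.** Table 1 and 4.1.9 place insertion at Week -2 (Day -14). A note under Table 1 says "ILR placement needs to be one week prior to baseline". In the text on the period after LINQ insertion, "The day of randomization will be denoted as Study Day 1".
- **Collection.** Section 6.4.1 and Table 1 footnote [8] begin AE collection at the first Lokelma dose; SAEs are reported from consent. The AE row of Table 1 has seven marks, the first under Accommodation Period 1. The SAE row has ten, including ILR Insertion.
- **Definition.** Section 6.1 says an AE can occur at any time, "including run-in or washout periods, even if no study treatment has been administered".
- **Causality.** Sections 6.4.3 and 6.4.4 ask about relationship to the study drug for every AE. They ask about relationship to study procedures for SAEs only.
- **Tabulation.** In 8.5.6 the TEAE window runs from the first dose to 14 days after the last dose in a 3K period, and from the first visit to 14 days after the last visit in a 2K period. It then says "Only TEAEs will be included in table summaries". Tables are by treatment group and study period. Per-patient listings cover all AEs and SAEs.
- **Removal.** Table 1 sets it between Day 141 and Day 155. Section 4.3 lets the patient keep the device.

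**The concern.** Most patients receive the recorder only because they joined the trial, and the protocol itself identifies its insertion as a source of harm. The collection rule, however, is tied to the drug and starts after the procedure. The definition in 6.1 would count a wound problem before Day 1 as an AE, but 6.4.1 does not collect it unless it is serious.

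The final report could therefore not give a complete complication rate for the implantation. The non-serious part cannot be recovered afterwards, because no analysis plan can tabulate events that were not recorded or use a causality answer that was not asked for.

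This is distinct from a second consequence of the same clause: patients who take the 2K bath first have no Lokelma dose until after cross-over. Moving the start of collection to Day 1 would address that problem but not this one, since implantation comes earlier still.

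**Working it through.** The plan states no figure on this point, so there is nothing to reproduce. The check sets the calendar against the collection and tabulation rules.

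**Implantation**

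| Step | Rule | Result |
|---|---|---|
| Insertion | Day -14, or one week before baseline | before Day 1 in every newly implanted patient |
| Non-serious AE collection opens | first Lokelma dose (6.4.1, footnote [8]) | no earlier than Day 1 |
| SAE collection opens | consent | insertion covered |
| TEAE window opens | first dose or first visit of a period (8.5.6) | no earlier than Day 1 |

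- Uncollected time for non-serious events, both sequences: Day -14 to Day -1 = 14 days, or about 7 days under the Table 1 note.
- A non-serious event starting in that time is recorded nowhere. A serious one is recorded and listed but appears in no table.
- A patient implanted but never randomized is also outside the Safety Analysis Set (8.3.3), on which all safety analyses are run.
- An insertion infection with onset on or after Day 1 can be a TEAE. It is then tabulated under the first-period bath.

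**Removal**

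Day 1 is a Monday or Tuesday, matching the patient's dialysis schedule. Period 2 is Days 71 to 140 (accommodation plus treatment phase). The removal window has 155 - 141 + 1 = 15 days.

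- *Period 2 = 3K.* Day 140 is an off-dialysis day on both schedules, so it is the last scheduled dose. The window closes on 140 + 14 = Day 154. Days 141 to 154 are inside: 14 of 15 (93%).
- *Period 2 = 2K.* The result depends on what the last visit is:
  - Week 20 visit: 1 + 19 × 7 = Day 134; closes Day 148; 8 of 15 (53%).
  - Last dialysis session: Day 138; closes Day 152; 12 of 15 (80%).
  - End of the period: Day 140; closes Day 154; 14 of 15 (93%).

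These are shares of calendar days. They are shares of removals only if removals are spread evenly over the window. A complication that begins some days after removal, or an early last dose, puts more events outside.

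**Possible number affected**

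The documents give no implant complication rate. Assuming 2% to 5%, 88 × 0.02 = 1.8 and 88 × 0.05 = 4.4 patients would have a complication. These are upper limits on the number missing from the tables among 88 newly implanted patients. They would be reached only if every event began before Day 1, which nothing in the protocol supports. Patients who enter with a usable recorder already in place (exclusion criteria 18 and 21) reduce the number further.

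**The case against.** The case for leaving the plan alone has several parts.

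- **Serious harms are not lost.** SAEs are collected from consent, carry procedure causality and are listed, so a count of serious complications is available. This stands. The loss is confined to non-serious events and to tabulation.
- **Table layout belongs to the SAP.** Section 8.5.6 defers full safety detail to it, and TEAE tables with full listings are a common convention. This stands for the extra table. It does not answer the collection rule or the missing causality item, which the protocol fixes.
- **The empty Baseline cell in Table 1 proves nothing.** Footnote [6] makes Baseline part of Week 1 of Accommodation Period 1, which has an AE mark. This is correct. The gap comes from 6.4.1 and footnote [8], and appears in the ILR Insertion column.
- **The bath comparison is hardly touched.** Implantation precedes randomization. Removal follows period 2 in both sequences, allocated 1:1, and the tables are descriptive. This stands.

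A reader might infer more than the documents support: that all removal harms are counted against the second bath, or that removal biases the comparison. The windows above cover only part of the removal days, removal is optional, and the named risk concerns insertion. A reader might also infer that no implant harm ever reaches a table; those starting on or after Day 1 can.

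**Conclusion.** The point holds for implantation. Non-serious implant harms starting before Day 1 are not recorded in either sequence, over about 7 to 14 days after the procedure. Serious ones are recorded and listed but excluded from every AE table by the TEAE restriction. Non-serious device events that are recorded later cannot be separated by investigator attribution.

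The removal part is minor. Coverage by the last TEAE window is 14 of 15 days after 3K and 8 to 14 of 15 after 2K, which depends on an undefined last visit and on the schedule being followed. The effect is some noise in descriptive tables.

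The number of events lost is unknown; the 1.8 to 4.4 patients above rest on an assumed rate and are an upper limit. Nothing here affects the primary analysis. The change is worth making because it concerns a risk the protocol itself names, costs little and cannot be made good after the data are collected.

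**What to change.** 1. **Collection.** Amend 6.4.1 and Table 1 footnote [8] so that AEs are recorded from ILR insertion, and add the AE mark in the ILR Insertion column. Adding the mark without changing the two texts would not start collection.
2. **Causality.** In 6.4.3 and 6.4.4, ask about relationship to study procedures for all AEs, as is already done for SAEs.
3. **Reporting.** In 8.5.6, add one table of device- and procedure-related AEs and SAEs from implantation to the last visit. Report it overall rather than by bath, for all implanted patients, including those never randomized.
4. **Leave the by-bath TEAE tables unchanged.** Taking events out of them on procedure attribution would let unblinded judgement in an open-label trial decide what enters the treatment comparison.

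The cost is one eCRF item, one extra table and slightly more AE recording before Day 1. No visits are added.

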### **8.5.7 Interim analysis**

No interim analysis is planned.

## **9. STUDY AND DATA MANAGEMENT**

### **9.1 Training of study site personnel**

Before the first patient is entered into the study, a Sponsor representative will review and discuss the requirements of the Clinical Study Protocol and related documents with the investigational staff and train them in any study-specific procedures.

The site PI will ensure that appropriate training relevant to the study is given to all study staff at their site, and that any new information relevant to the performance of this study is forwarded to the staff involved.

The site PI will maintain a record of all individuals involved in the study (medical, nursing, and other staff).

## **9.2 Monitoring of the study**

Site management and monitoring will be the responsibility of the Sponsor (NephroNet). During the study, a Sponsor representative will have regular contacts with the study sites, including visits to:

- Provide information and support to the Investigator(s)
- Confirm that facilities remain acceptable
- Confirm that the investigational team is adhering to the protocol, that data are being accurately and timely recorded in the eCRFs, that biological samples are handled in accordance with the Laboratory Manual and that study drug accountability checks are being performed
- Perform source data verification (a comparison of the data in the eCRFs with the patient's medical records at the hospital or practice, and other records relevant to the study), including verification of informed consent of participants. This will require direct access to all original records for each study patient (e.g., clinic charts)

The Sponsor representative will be available between visits if the Investigator(s) or other staff at the study site needs information and advice about the study conduct.

### **9.2.1 Source data**

Refer to the Research Agreement for location of source data.

### **9.2.2 Research Agreement(s)**

Site PIs should comply with all the terms, conditions, and obligations of the Research Agreement, or equivalent, for this study. In the event of any inconsistency between this Clinical Study Protocol and the Research Agreement, the terms of the Clinical Study Protocol shall prevail with respect to the conduct of the study and the treatment of patients. In all other respects, not relating to study conduct or treatment of patients, the terms of the Research Agreement shall prevail.

Agreements between the Sponsor and the site PI should be in place before any study-related procedures can take place, or patient are enrolled.

### **9.2.3 Archiving of study documents**

The Sponsor follows the principles outlined in the Research Agreement (RA).

The study site/site PI will retain the essential documents specified in the Good Clinical Practice (GCP), guidelines of the International Conference on Harmonisation (ICH) (e.g., source document such as medical records, contract, signed consent form). Essential documents should be retained at the study site as per regulatory obligations for a Phase IV clinical trial, and thereafter destroyed after approval from the Sponsor.

### **9.2.4 Deviation from the clinical study protocol**

The Investigator(s) must not deviate from or make any changes to the protocol without documented approval from the Sponsor and the reviewing IRB, except in case of a medical

emergency, where the deviation or change is necessary to avoid an immediate hazard to study patients. In such case, the site PI must provide details of the deviation or change (including reason), and the proposed revision(s) to the protocol, to the Sponsor and IRB as soon as possible, in order to obtain their approval.

All deviations from the protocol should be documented in the eCRF regardless of their reasons.

### **9.3 Study Timetable and End of Study**

The end of the study is defined as Last Patient Last Visit (LPLV).

The study is expected to start in April 2022 and to end by end of June 2023.

The study may be terminated at individual centers if the study procedures are not being performed according to GCP, or if recruitment is slow. The Sponsor may also terminate the entire study prematurely if concerns for patient safety arise within this study.

